**Study start: July 17, 2020**

**Primary completion: October 1, 2021**

**Study completion: October 2, 2021**

#### **Brief summary**

A retrospective consecutive population of patients treated with conical tapered stems in cementless total hip arthroplasty for osteoarthritis due to congenital hip pathologies will be selected. The aim of this retrospective study is to evaluate the long-term clinical and radiographic results of this implant and the survival rates in such a specific cohort.

#### **Study description**

Congenital hip pathologies may severely alter the local anatomy of the hip, making total hip arthroplasty (THA) due to osteoarthritis after congenital hip pathologies challenging. While it seems that congenital hip pathologies did not significantly influence the outcomes when compared to THA after osteoarthritis, the choice of implant was demonstrated to impact the survival rates of the THA after congenital hip pathologies.

To date, no guidelines exist about the correct choice of hip implant in congenital hip pathologies: only mid-term case series are available. Conical tapered stems have been frequently suggested for the most difficult cases.

The aim of this study is to describe the survival rates and the long-term clinical and radiological outcome of conical tapered stems in THAs after congenital hip pathologies.

#### **Population**

retrospective, consecutive adult population treated with conical tapered stems in cementless total hip arthroplasty for osteoarthritis due to congenital hip pathologies.

Inclusion Criteria:

Symptomatic hip osteoarthritis due to congenital hip pathologies

Consecutive population with a minimum follow-up of 2 years

Cementless total hip arthroplasty with conical tapered stem

Pre-operative planning using CT

Complete clinical and radiographic assessment

Exclusion Criteria:

Other type of hip osteoarthritis

Other type of implants

Inadequate pre-operative planning (eg: no CT)

Incomplete clinical and radiographic assessment

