#### **Methods**

Demographics of the patients involved were collected using medical records.

The patients were clinically and radiographically evaluated in the post-operative setting at 1, 6, 12, 24 months and then biennial. Harris Hip score (HHS) was adopted to clinically assess the patients at the final follow-up []. Plain antero-posterior pelvis radiographs were taken at every follow-up: the last X-ray was evaluated for the positional parameters specified in the table []. Osseointegration was evaluated using the criteria of Moore et al. (cup) and Engh et al. (stem) [].

Failures were collected and the survival rates were specified, using a 95% confidence interval.

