#### **Statistical analysis plan**

Statistical analysis has been done by using Windows SPSS 14.0, 14.0.1 version (SPSS Inc, Chicago, IL) and JMP, 12.0.1 version (SAS Institute Inc, Cary, NC, 1989-2007).

The quantitative data were expressed as average values, standard deviations and ranges of minimum and maximum. The qualitative data were expressed as frequencies and percentages. The survivorship of the primary THA implants were calculated and plotted according to Kaplan-Meier method (95% confidence interval). The endpoint was removal or change of any component. The implants were followed until the last date of observation (date of death or 31 December 2019). A p-value less than 0.05 was considered statistically significant.

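### Complete assessment and 2-year minimum follow-up are entry conditions for the only population defined, so the Kaplan-Meier analysis can lose hips that should be events or be censored

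*Combined protocol and SAP*

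**What the plan says.** The Population section defines one study population. Its inclusion list contains "Consecutive population with a minimum follow-up of 2 years" and "Complete clinical and radiographic assessment", and its exclusion list repeats the second as "Incomplete clinical and radiographic assessment". The section does not define completeness, and it does not say whether the 2 years are time since surgery or follow-up actually achieved.

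The Methods section describes what is assessed: "Harris Hip score (HHS) was adopted to clinically assess the patients at the final follow-up", and for the radiographs "the last X-ray was evaluated for the positional parameters". It adds that "Failures were collected and the survival rates were specified", without saying which hips were searched for failures.

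The Statistical analysis plan applies Kaplan-Meier to the primary implants. It states: "The endpoint was removal or change of any component". Observation ends at death or on 31 December 2019. No separate survival set is defined, no exemption is made for hips that were revised, lost or in patients who died, and there is no rule for a hip whose last contact came before the closing date.

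**The concern.** Survival is a stated aim in both the Brief summary and the Study description. Kaplan-Meier deals with incomplete observation by censoring: a hip contributes until its implant status is last known. An entry rule that depends on what happened after surgery removes such hips instead.

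The completeness rule is the more serious of the two. The only clinical score and radiographic readings that the Methods section describes are post-operative, so the rule appears to depend at least partly on later attendance. Neither reading is needed to know whether a component was removed or changed.

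The bias can go either way. The curve moves up if revised hips are less often complete. It moves down if unrevised hips that were lost, or whose patients died, are removed while revised hips stay. It does not move if completeness is unrelated to revision.

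The 2-year rule matters only if it means achieved follow-up and hips revised before 2 years are dropped. Two-year survival is then 100% by construction.

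**Working it through.** The documents give no sample size, event count, revision rate or survival figure, so there is no figure of the plan's own to reproduce. Every rate below is an assumption, chosen to show possible sizes.

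**Reference case.** Assume 2% of hips are revised by 2 years and 0.5% per year after that. True 10-year survival is 0.98 × exp(-8 × 0.005) = 0.9416, so cumulative revision is R = 0.0584.

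**Completeness differs between revised and unrevised hips.** If a share a of revised hips and a share b of unrevised hips are complete, apparent survival is (1 - R)b / [R·a + (1 - R)b]. With b = 0.90:

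| Revised hips complete (a) | Calculation | Apparent 10-year survival | Shift (points) |
|---|---|---|---|
| 90% | 0.8474 / (0.0526 + 0.8474) | 94.2% | 0 |
| 70% | 0.8474 / (0.0409 + 0.8474) | 95.4% | +1.2 |
| 50% | 0.8474 / (0.0292 + 0.8474) | 96.7% | +2.5 |
| 100% | 0.8474 / (0.0584 + 0.8474) | 93.6% | -0.6 |

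**Unrevised hips dead or lost before the closing date are dropped, all revised hips kept.** This was simulated with 3,000,000 hips, uniform potential follow-up and exponential time to death or loss. Keeping all hips and censoring correctly returned about 94.2%, as it should.

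| Potential follow-up | 2% per year dead or lost | 5% per year dead or lost |
|---|---|---|
| 2 to 12 years | 93.7% (-0.4) | 93.0% (-1.2) |
| 2 to 18 years | 93.3% (-0.8) | 92.0% (-2.2) |
| 2 to 25 years | 93.0% (-1.2) | 90.9% (-3.3) |

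If all dead or lost hips are dropped whether revised or not, the shift is 0.

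**Two-year rule.** If it is defined by date of surgery, the shift is 0. If revisions before 2 years are dropped, apparent 10-year survival is exp(-0.04) = 0.9608, a shift of +1.9. In general the shift is e × exp(-8h), where e is the early revision risk and h the later yearly rate. It runs from 0.01 × exp(-0.08) = +0.9 to 0.04 × exp(-0.024) = +3.9 points.

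**Would a curve starting at 2 years repair both?** Its true value at 10 years is 96.1%. With completeness of 50% against 90% it reads 0.9608 × 0.9 / (0.0392 × 0.5 + 0.9608 × 0.9) = 97.8%. With unrevised dead or lost hips dropped (follow-up 2 to 18 years) it reads 95.6% at 2% per year and 94.8% at 5%. It therefore does not repair the completeness selection.

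**The case against.** The link from completeness to later attendance is inferred. In both lists the item follows CT planning, so it may partly concern baseline records. The final follow-up and the last film may also mean the last available ones; a hip revised at 14 months would then still have both and need not fail. Naming death as an end of observation suggests that at least some deceased patients were meant to stay in and be censored, so the scenario that drops every unrevised dead or lost hip fits the plan poorly for deaths, though it remains possible for losses. The illustration pools the two, so its figures cannot be split.

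On the 2-year rule, the word consecutive, the common closing date and the collection of failures with no lower time limit all favour the harmless reading. Finally, the illustrated shifts span zero and cannot be set against the width of the confidence interval, because no sample size is given.

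These points stand as limits on the likely bias. They do not override an explicit exclusion criterion that applies to the only population defined, and no passage says that revised, dead or lost hips are exempt. The missing rule for loss to follow-up would be a gap even without the two criteria, but it leaves the handling of these hips still less certain.

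**Conclusion.** The concern holds. As written, the entry criteria allow hips to be removed that the survival analysis should count or censor; the documents do not show that any were. Completeness is the main issue, and the 2-year rule may need only clarification.

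Under the assumed rates, selection on completeness moves 10-year survival by anything from -3.3 to +2.5 points, with no shift in some scenarios. Dropping early revisions would move it by +0.9 to +3.9. These figures show what is possible; the effect in this cohort cannot be determined from the documents. Where cumulative revision is only a few percent, shifts of this order could matter. The point should be fixed. Confidence is medium, because the meaning of both criteria has to be inferred.

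**What to change.** - For survival, include every consecutive, otherwise eligible hip operated on or before 31 December 2017 (2 years before the closing date), whatever its later outcome or attendance. Do not apply the completeness criterion to this set.
- Count every revision from the day of surgery. Censor the remaining hips at last known implant status: death, last contact or 31 December 2019.
- Keep the completeness and 2-year criteria for the Harris Hip Score and radiographic summaries only, and define what complete means.
- Report how many hips each criterion removes, split into revised, dead, lost and other.
- If hips removed by the 2-year rule cannot be recovered, start the curve at 2 years and label it conditional on reaching that point. This answers the 2-year rule only. Hips removed for incompleteness must still be restored, or the curve reported as potentially biased alongside the exclusion counts.

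The cost is a record check of the hips screened out by the two criteria, a re-run of the curve (the Statistical analysis plan describes the analysis as already performed) and possibly a slightly less favourable estimate. If the 2-year rule already means time since surgery, that part needs one clarifying sentence.

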#### **Methods**

Demographics of the patients involved were collected using medical records.

The patients were clinically and radiographically evaluated in the post-operative setting at 1, 6, 12, 24 months and then biennial. Harris Hip score (HHS) was adopted to clinically assess the patients at the final follow-up []. Plain antero-posterior pelvis radiographs were taken at every follow-up: the last X-ray was evaluated for the positional parameters specified in the table []. Osseointegration was evaluated using the criteria of Moore et al. (cup) and Engh et al. (stem) [].

Failures were collected and the survival rates were specified, using a 95% confidence interval.

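### HHS and radiographic assessment are not stopped at revision, so those summaries may describe a replaced component, or survivors only

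*Combined protocol and SAP*

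**What the plan says.** The Study description sets the aim: to "describe the survival rates and the long-term clinical and radiological outcome of conical tapered stems in THAs after congenital hip pathologies". The object of all three outcomes is therefore the conical stem.

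The Methods section gives the timing of the clinical and radiographic measurements:

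- Clinical score: "Harris Hip score (HHS) was adopted to clinically assess the patients at the final follow-up".
- Position: "the last X-ray was evaluated for the positional parameters specified in the table".
- Osseointegration: criteria are named for cup and stem, but no film or time point is given.
- Visits: "The patients were clinically and radiographically evaluated in the post-operative setting at 1, 6, 12, 24 months and then biennial". Pelvic films were taken at each of these visits; HHS is stated only for the last one.

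The Statistical analysis plan section defines failure: "The endpoint was removal or change of any component". The definition sits within the Kaplan-Meier analysis of the primary implants. Observation ends at death or at the close of 2019; revision is not listed as an end of clinical or radiographic assessment. Quantitative data are summarised by mean, standard deviation and range.

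The Population section requires at least two years of follow-up and excludes patients whose clinical and radiographic data are incomplete. It does not say how a revised hip stands against either criterion.

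**The concern.** The survival analysis is tied to the primary implant, but the HHS and radiographic summaries are tied to the patient's last visit. The two part company in exactly the hips where the implant failed. Take a hip whose stem was exchanged at year 4 and which is last seen at year 10. Under the Methods as worded, its HHS is that of a re-operated hip and its last film shows a different stem. The alternative, leaving such hips out, restricts the summaries to implants that survived.

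Clinical and radiographic results are two of the three outcomes named in the aim. As the plan stands, a reader could not tell which implant, or which hips, those results describe.

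**Working it through.** **Is the gap real?** Setting the sections side by side:

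| Outcome | Time point stated | Stopped at revision? |
|---|---|---|
| Survival | Time to revision of any component | Yes: revision is the event |
| HHS | Patient's last visit | Not stated |
| Position | Last film | Not stated |
| Osseointegration | None | Not stated |

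No section says whether a revised hip enters the lower three rows with its value before revision, its value after revision, or not at all.

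**Which component is affected?** The failure definition covers every component. If the stem or cup was exchanged, the last film shows a different stem or cup. If only the head or liner was exchanged, or only the cup, the original stem is still on the last film and can be read there.

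**Size for mean HHS.** The plan states no sample size, revision rate or HHS value, so there is no figure to reproduce and every input below is an assumption. Let r be the share of hips revised, U the mean HHS in unrevised hips, *pre* the score of a failing hip before revision and *post* its score afterwards. The reference is the mean over all hips with the original implant scored:

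reference = (1 − r) × U + r × pre

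*Revised hips left out.* The reported mean is U, so the shift is r × (U − pre). With r = 5–15%, U = 88, pre = 50–60:

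- smallest: 0.05 × (88 − 60) = 1.4 points
- largest: 0.15 × (88 − 50) = 5.7 points

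The shift is upward whenever pre is below U.

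*Replacement scored.* The shift is r × (post − pre). With post = 75–80 and pre = 50–60 it runs from 0.05 × (75 − 60) = 0.75 to 0.15 × (80 − 50) = 4.5 points, but the positive sign comes from assuming post above pre.

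*Wider inputs* (U = 90, pre 50 or 70, post 45–85, r = 2–15%):

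| Handling | Lowest shift | Highest shift |
|---|---|---|
| Left out | 0.02 × (90 − 70) = +0.4 | 0.15 × (90 − 50) = +6.0 |
| Replacement scored | 0.15 × (45 − 70) = −3.75 | 0.15 × (85 − 50) = +5.25 |

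At r = 5% alone, leaving hips out gives +1.0 to +2.0, and scoring the replacement gives −1.25 to +1.75.

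**Osseointegration.** If, and only if, it is read on the last film, a stem revised for loosening cannot appear there as a fixation failure. The overstatement is then at most the share of stems revised for loosening, which the documents do not give.

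**Position.** The error is measuring a different component. Nothing in the documents gives it a direction.

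**The case against.** The strongest reply is that the plan is silent rather than wrong. The Statistical analysis plan speaks of primary implants and of following the implants, and the Population section excludes other implant types, so the investigators may have meant the index implant throughout. That reading is plausible but nowhere stated. The Methods do state a timing rule, and that rule refers to the patient's last visit and last film. The objection stands to this extent: the documents do not show that replacements were in fact scored.

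Second, failures are not hidden. They are collected and counted in the Kaplan-Meier analysis, so a reader sees how many implants failed. This stands for survival. It does not tell the reader what the HHS and radiographic figures describe.

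Third, with few revisions the effect on mean HHS is small, as the 5% row of the working shows. This also stands.

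Fourth, HHS before revision may not exist, because scoring is stated only for the last visit. So a repair cannot rely on it. The one proposed does not.

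Finally, restricting the HHS mean to unrevised hips does not by itself remove the bias. On the first set of assumptions, moving from scored replacements to that mean raises it by 0.05 × (88 − 80) = 0.4 to 0.15 × (88 − 75) = 1.95 points. This is correct, and it is why that mean needs a label, a count and a companion measure.

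**Conclusion.** The point holds as a gap in the stated rules. HHS and position are not stopped at revision, osseointegration has no stated film, and revision is used only in the survival analysis. If revised hips are left out (for instance as incompletely assessed), mean HHS is too high whenever failing hips score below unrevised ones: about 1.4 to 5.7 points on the assumed inputs, none of which comes from the documents.

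Four stronger readings are tempting and are not supported:

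- *The conical stem's results look better than they were under either handling.* The direction is fixed only for leaving hips out. If the replacement is scored it depends on whether HHS after revision is above or below HHS before it. For position no direction can be claimed.
- *Osseointegration will read 100% beside a survival curve with stem failures.* That needs a last-film rule, which the Methods state for position and not for osseointegration. Earlier films exist on which a loose stem could be graded.
- *Every revision puts a different stem on the last film.* Failure covers any component, so the original stem can remain in place.
- *Survival is biased too.* It is not; revision is its event.

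This should be corrected. It bears on the interpretation of two of the three outcomes in the aim, not on the validity of the study as a whole.

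**What to change.** Amend the Methods section as follows.

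1. For each component removed or changed, read its position and osseointegration on the last film before that revision, and count a component revised for loosening as not osseointegrated. Read components left in place on the last film.
2. Report mean HHS for hips with the original implant in place, labelled as survivors only. State how many revised hips lie outside that mean, and show their HHS after revision separately.
3. Beside it, report the proportion of all hips that are unrevised and reach one HHS threshold, fixed before analysis, with revised hips counted as failures.

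Give the number of hips behind each summary.

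The cost is wording and re-reading existing films for the revised hips, since films were taken at every visit; no new visits are needed. Osseointegration and the HHS success proportion may become less favourable. The survivors-only mean will not fall: it is unchanged if revised hips were already left out, and rises if replacements had been scored and scored below unrevised hips. For that reason it must not be presented alone.

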#### **Statistical analysis plan**

Statistical analysis has been done by using Windows SPSS 14.0, 14.0.1 version (SPSS Inc, Chicago, IL) and JMP, 12.0.1 version (SAS Institute Inc, Cary, NC, 1989-2007).

The quantitative data were expressed as average values, standard deviations and ranges of minimum and maximum. The qualitative data were expressed as frequencies and percentages. The survivorship of the primary THA implants were calculated and plotted according to Kaplan-Meier method (95% confidence interval). The endpoint was removal or change of any component. The implants were followed until the last date of observation (date of death or 31 December 2019). A p-value less than 0.05 was considered statistically significant.

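### The Kaplan-Meier 95% interval is per implant and nothing limits a patient to one hip; if correlated bilateral hips are included, it is slightly too narrow

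*Combined protocol and SAP*

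**What the plan says.** The Statistical analysis plan makes the implant the unit of analysis: "The survivorship of the primary THA implants were calculated and plotted according to Kaplan-Meier method (95% confidence interval". Follow-up is also counted per implant: "The implants were followed until the last date of observation (date of death or 31 December 2019". The event is any component being removed or exchanged. The Methods section repeats the confidence level: "Failures were collected and the survival rates were specified, using a 95% confidence interval".

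The Brief summary describes the cohort in terms of people: "A retrospective consecutive population of patients treated with conical tapered stems". The Population section lists five inclusion and four exclusion criteria. Most of them are worded for the hip or the procedure, for example "Symptomatic hip osteoarthritis due to congenital hip pathologies". None restricts a patient to one hip, so a second hip that met the criteria would qualify in a consecutive series.

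No section gives the number of patients or hips, states that the two are equal, or describes a clustered variance, a frailty model or a one-hip-per-patient analysis.

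**The concern.** The usual Kaplan-Meier (Greenwood-type) variance assumes independent observations. Two hips in one patient share that patient's bone quality, activity and anatomy, so their failures may be positively correlated. If such pairs are in the data, they carry less information than the same number of hips from different patients, and the interval overstates the precision.

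The Study description gives survival as an aim: "The aim of this study is to describe the survival rates and the long-term clinical and radiological outcome of conical tapered stems". The 95% interval is the only measure of uncertainty attached to it, so a reader relies on that interval to judge how firmly the survival rate is known. The concern is limited to the interval: the implant is a suitable unit for the estimate.

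**Working it through.** **No figure to reproduce.** The documents state no sample size, number of failures, survival estimate, bilateral share or interval formula. The check therefore establishes direction in general and size under stated assumptions.

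**Inputs from the documents.** Unit: implant. Confidence level: 95% (z = 1.96, taken as two-sided). Censoring at death or a fixed calendar date. Minimum follow-up: 2 years.

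**Assumed inputs.** Greenwood variance; share p of patients with two hips; within-patient correlation of failure status (ICC).

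**Analytic check.** With at most two hips per patient, the share of hips that belong to bilateral patients is q = 2p/(1+p). The variance is multiplied by DE = 1 + ICC × q, and the correct width is √DE times the naive width.

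- p = 0.3: q = 0.6/1.3 = 0.462. ICC 0.13 gives DE = 1.060 and a ratio of about 1.03; ICC 0.32 gives DE = 1.148 and about 1.07.
- p = 0.4: q = 0.8/1.4 = 0.571. The same ICCs give DE = 1.074 and 1.183, ratios of about 1.04 and 1.09.
- p = 0.1: q = 0.2/1.1 = 0.182. ICC 0.1 to 0.3 gives ratios of 1.009 to 1.027.
- Theoretical limit, p = 1 and ICC = 1: DE = 2 and ratio 1.414. A nominal 95% interval would then cover 83.4%.

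DE exceeds 1 whenever p and ICC are both positive, so the direction is certain under those conditions.

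**Simulation.** 100 patients, 10% failure at 10 years, exponential failure times, Gaussian latent correlation within patient, censoring uniform over 2 to 20 years and shared within patient, 60,000 replicates per cell. Half-widths are in percentage points at 10 years.

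| Bilateral | Latent correlation (ICC) | True SE / Greenwood SE | Due to clustering alone | Half-width: Greenwood, true | Unclustered log-log coverage |
|---|---|---|---|---|---|
| 30% | 0 | 1.017 | – | 5.71, 5.81 | 95.4% |
| 30% | 0.3 (0.13) | 1.041 | 1.024 | 5.71, 5.95 | 94.8% |
| 30% | 0.6 (0.32) | 1.076 | 1.058 | 5.71, 6.14 | 94.1% |
| 40% | 0 | 1.014 | – | 5.51, 5.59 | 95.4% |
| 40% | 0.3 (0.13) | 1.048 | 1.033 | 5.51, 5.77 | 94.7% |
| 40% | 0.6 (0.32) | 1.092 | 1.076 | 5.51, 6.02 | 93.8% |

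The rows with zero correlation show that about 0.1 point of the gap has nothing to do with clustering. Net of that, clustering adds between 5.95 − 5.81 = 0.14 and 6.02 − 5.59 = 0.43 points. Mean estimated survival was 0.900 throughout, so the estimate is unbiased.

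**Does clustering the variance repair it?** On the log-log scale, a patient-clustered robust variance gave 94.9% to 95.1% coverage in all these cells. On the plain scale it gave only 92.3% to 92.7%. Plain Greenwood covers just 92.2% with no bilateral patients at all, so most of the plain-scale shortfall comes from few events. A percentile bootstrap that resamples patients gave 92.9% to 93.2%.

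**Sensitivity.** At 30% bilateral and latent correlation 0.3 / 0.6, clustering alone gives 1.020 / 1.058 with 50 patients, 1.028 / 1.061 with 200 patients, and 1.024 / 1.064 with 100 patients and 5% failure. An unfavourable case (40% bilateral, ICC 0.5) gives a total ratio of 1.134; log-log coverage is 92.8% unclustered and 95.0% clustered. A different model (shared gamma frailty, 600 hips, failure correlation about 0.05 to 0.34) gives ratios of about 1.02 to 1.06 at 20% bilateral and 1.04 to 1.10 at 50%.

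**The case against.** The strongest reply is that no defect has been shown. No section says that any patient contributed two hips, counting implants is ordinary wording for device survivorship, and positive correlation is not documented either. This stands, and it is why the point is conditional.

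The second reply is that the 30% to 40% range was chosen freely. At 10% bilateral and ICC 0.1 the widening is only 0.9%. In further runs of the same set-up (12,000 replicates, noise about 0.2 points), the unclustered log-log interval needed no repair. With 100 patients, 10% bilateral and latent correlation 0.3, coverage was 95.2% unclustered and 95.0% clustered. With 20% bilateral it was 94.9% and 94.8%. With 50 patients and 30% bilateral it was 96.1% and 95.8%. This also stands: the variance is still understated in those cells, but coverage suffers visibly mainly when bilaterality and correlation are both high.

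Third, the log-log scale addresses few events rather than clustering, and that interval is undefined if there are no failures. Both are true. They bear on how to carry out the fix and do not remove the dependence.

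Finally, the study is descriptive and nothing is decided on the interval. That limits the severity of the point without making the interval correct.

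**Conclusion.** The point holds as a minor, conditional one. The analysis is per implant, eligibility sets no one-hip limit, and two hips from one patient are not addressed. If correlated bilateral hips are present, the ordinary interval is too narrow. Under the main assumptions the total understatement of the standard error is 4% to 9%, of which clustering accounts for 2% to 8%. It would be smaller with few bilateral patients, larger if most were bilateral with strongly correlated failures, and zero if every patient contributed one hip. The conclusion assumes that the unnamed interval formula is the standard one. The survival estimate is not affected.

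**What to change.** 1. Report the number of patients and the number of hips. This alone settles whether the issue arises.
2. If every patient contributes one hip, say so and make no cluster adjustment.
3. If any patient contributes two, keep the implant as the unit for the Kaplan-Meier estimate and calculate its 95% interval with a robust variance clustered on patient, on the log-log scale. A bootstrap that resamples patients is an alternative, but its simple percentile form covered only about 93% in the assumed set-up. A first-hip-only analysis is optional.

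The cost in precision is small. On the log-log scale the half-width rises from 5.98 to between 6.08 and 6.31 points at 30% bilateral, and from about 5.75 to between 5.87 and 6.15 at 40%, so by roughly 0.1 to 0.4 points.

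Some code is needed, possibly outside the packages named in the SAP ("Statistical analysis has been done by using Windows SPSS 14.0, 14.0.1 version (SPSS Inc, Chicago, IL) and JMP, 12.0.1 version"), because the documents do not show whether those versions offer a clustered Kaplan-Meier variance. Each hip must be linked to its patient. The Methods section says "Demographics of the patients involved were collected using medical records", so this should be possible.

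### Must the plan state the type of Kaplan-Meier 95% confidence interval and a rule for zero failures?

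*Combined protocol and SAP*

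**What the plan says.** The Study description puts implant survival first among its aims: "The aim of this study is to describe the survival rates and the long-term clinical and radiological outcome". The Statistical analysis plan section gives the estimator and confidence level: "The survivorship of the primary THA implants were calculated and plotted according to Kaplan-Meier method (95% confidence interval". It defines the event, "The endpoint was removal or change of any component", and the end of observation, "The implants were followed until the last date of observation (date of death or 31 December 2019". The Methods section repeats the confidence level: "Failures were collected and the survival rates were specified, using a 95% confidence interval".

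Neither section names a variance formula, a transformation or an exact method, a time point at which survival is quoted, or what is shown if nothing fails. The software sentence, "Statistical analysis has been done by using Windows SPSS 14.0, 14.0.1 version (SPSS Inc, Chicago, IL) and JMP, 12.0.1 version", names two packages and ties neither to the interval. Survivorship is counted by implant, while the Population section describes a "retrospective, consecutive adult population treated with conical tapered stems" and does not say whether a patient may contribute two hips. No cohort size, failure count or expected survival is given anywhere.

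**The concern.** Survival is a main result of a single-cohort study, so its interval is most of the inference a reader will take away. If hip stems rarely fail, the symmetric Greenwood interval behaves badly: its lower limit is too high, its upper limit can exceed 100%, and with no failures it shrinks to 100% at both ends. A log-log interval is better once a failure has occurred but cannot be computed before that. A plan silent on all this could let a report overstate how well implant survival is known. If some patients have both hips in the cohort, the ordinary variance also treats those hips as independent.

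**Working it through.** There is no figure in the plan to reproduce. From the documents come the estimator, the 95% level (taken as two-sided, z = 1.96), the event and the end of observation. Hips, failures, true survival and share of bilateral cases are assumed and varied.

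**1. Interval limits, n = 100 hips, no earlier censoring.** Here Greenwood's variance reduces to S(1 − S)/n.

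- Symmetric: S ± 1.96·√(S(1 − S)/n). With 3 failures, 0.97 ± 1.96·√(0.97 × 0.03/100) = 0.97 ± 0.0334, that is 93.7% to 100.3%.
- Log-log: S^exp(±1.96·se), with se = √((1 − S)/(nS))/|ln S|. With 3 failures, se = 0.01759/0.03046 = 0.577, giving 91.0% to 99.0%.
- Exact: Clopper-Pearson.

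| Failures of 100 | Symmetric lower | Log-log lower | Exact lower |
|---|---|---|---|
| 0 | 100% | undefined (0/0) | 0.025^(1/100) = 96.4% |
| 1 | 97.0% | 93.1% | 94.6% |
| 3 | 93.7% | 91.0% | 91.5% |
| 5 | 90.7% | 88.4% | 88.7% |

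With 3 to 5 failures the symmetric limit lies 2.0 to 2.2 points above the exact limit. With 50 hips and no failure the exact lower limit is 0.025^(1/50) = 92.9%.

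**2. Coverage, no censoring.** Exact binomial coverage over n = 50 to 150 (step 1) and true survival 90% to 99% (step 0.1 point):

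- Symmetric: 39.5% to 95.4%, mean 88.6%, with 39.7% of settings below 90%.
- The lowest value is at n = 50 and survival 99%. There the chance of no failure is 0.99^50 = 60.5%, and 39.5% + 60.5% = 100%, so the misses come almost entirely from samples without failures.
- Restricted to n = 100 to 150 and survival 90% to 95%: mean 92.6% for symmetric and 95.8% for log-log.
- At n = 200 with 5% or 10% failing: 92.6% and 92.7% for symmetric.

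**3. Coverage with staggered follow-up.** Simulation with exponential failures, follow-up uniform on 2 to 15 years, survival read at 10 years:

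| Hips | 10-year failure | Chance of no failure | Symmetric coverage |
|---|---|---|---|
| 50 | 2% | 47% | 52.9% |
| 100 | 2% | 22% | 78.1% |
| 100 | 10% | about 0% | 90.9% |
| 200 | 5% | about 0% | 91.6% |
| 200 | 10% | 0% | 93.3% |

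**4. Two hips in one patient.** The design effect is 1 + f·r, with f the share of hips in pairs and r the within-patient correlation. For f = 0 to 0.4 and r = 0 to 0.5 it runs from 1.00 to 1.20. The interval is then too narrow by 1 − 1/√1.20 = 8.7% at most, and by nothing if there are no pairs.

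**5. Would a fixed rule be better?** A natural rule is log-log when there are failures and otherwise 0.025^(1/m), with m the patients still at risk. Under the follow-up of step 3, with 10-year survival 99%, 40% of hips in pairs and independent failures, the mean lower limit for 100 hips is about 88.5% with no failures and 90.9% with one. For 50 hips it is about 78% and 83%. The rule reports a cohort without failures as less certain than one with a failure.

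**The case for a change.** The strongest case for a change is that survival is the first-named aim, the text leaves the method open, and neither package is tied to the interval. If 10-year failure were 2%, a cohort of 50 or 100 hips would have no failure by then in 47% or 22% of cases, so a zero-failure rule would be a practical need. Adding log-log and an exact zero-failure bound brings coverage on the grid in step 2 to between 91.1% and 98.5%, for two sentences of wording and a short re-analysis.

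The omission stands, and so does the arithmetic for few failures. Three things do not carry over into a change.

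- Few failures and a symmetric interval are both assumed. The event covers any component and the aim is long-term, so failures need not be rare. If log-log was used and at least one implant failed, stating it changes no result.
- The worst coverage figures come mainly from samples without failures. An interval of 100% to 100%, or none at all, is plain on the page, and an analyst would replace it with an exact limit or report the number at risk.
- A prescribed rule has its own faults, as step 5 shows, and depends on a time point that the plan does not fix.

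**Conclusion.** The concern does not call for a change. Estimator, confidence level, event and end of observation are all stated; leaving the transformation to the analyst is an ordinary level of detail for a descriptive retrospective series. The plan gives a significance level, "A p-value less than 0.05 was considered statistically significant", but names no test or comparison that uses the survival interval, and the point estimate is untouched.

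The likely size is modest: about 2 points on the lower limit with 3 to 5 failures in 100 hips, and mean symmetric coverage of 92.6% against a nominal 95% over 100 to 150 hips with survival of 90% to 95%. It is larger for cohorts near 50 hips with survival of 97% or more. Clustering adds at most about 9% to the narrowing under the assumed ranges. All of this rests on assumed cohort sizes and failure rates, and on a symmetric interval that the documents do not say was used.

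The analysis section is written in the past tense, so new wording would record a choice already made rather than prespecify one. The report can give the interval type, the time points quoted, the hips and patients at risk at each, and the number of bilateral cases, which lets a reader judge the interval without any amendment.
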